#### 5.13.5 Caregiver and patient activity

The accelerometer data of each subject will be transformed into a low-dimensional representation using motif discovery algorithms. Such techniques are completely data-driven, and search for motifs (i.e., patterns) in the data that occur more often than chance. A signal can then be represented by the number of times a particular motif occurs. Others have successfully used such techniques for representing a variety of waveform data, including accelerometer and continuous glucose data. The accelerometer data will be processed to derive estimates of total sleep duration (i.e., hours per night), wake after sleep onset, and sleep efficiency (i.e., ratio of sleep to wake). The variables will be compared between arms.

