### 2.5.4 Wearable Sensor Device (Fitbit)

Each participant (caregiver, patient) will be given a wearable sensor to wear throughout the treatment period, except while in water or when charging. The goal is to collect objective, continuous, multi-parameter physiological data (e.g., total hours of sleep, sleep quality, total number of steps) on caregivers and patients throughout the treatment period to correlate with their subjective, snapshot caregiver- and patient-reported outcomes collected at three time points throughout the Intervention Period (baseline, and days 30 and 120 post-BMT). Participants will receive an instruction manual on how to charge and conveniently download data from the device. The data will be backed up to a HIPPA-secure data repository. For troubleshooting, detailed instructions will be provided for all participants, and customer support will be available 8AM – 5PM CST. Our team is available by pager after hours, if needed. Participants may use any Fitbit they may already have if they do not want to use the study provided Fitbit. Our study team will not be replacing any lost or broken Fitbit once a participant has reached Day 120 on study.

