#### 5.13.6 Caregiver and patient health care utilization

The total count of hospital days, ED visits, readmissions, and ambulatory care clinic visits within the first 120 days post-BMT, with adjustment for follow-up, will be compared between arms using a Poisson regression model, with adjustment for potential mediating or moderating effects of patient or caregiver characteristics, if needed. The data will be captured at the time of PRO assessments. Subjects will remain in follow-up for 1-year post-HCT. The study team will have access to the electronic medical record for 1-year post-HCT.

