## **APPENDICES**

### **APPENDIX A: FITBIT CHARGE 3**

The Fitbit Charge 3 is a smart watch capable of measuring heart rate, exercise amount, and sleep levels. There is a retail version available, and that is the model we will be using for our study. The data collected by the Fitbit Charge 3 is transferred from the smart watch to the Fitbit application installed on the patient's phone via Bluetooth Low Energy (BLE), a form of Bluetooth specifically designed to lower power consumption without compromising range. The app then transmits the data to Fitbit's information management system securely and without identifiable information. The smart watch can be worn on either wrist to give accurate measurements. The Charge 3 is made of safe-to-use aluminum and flexible, non-elastic elastomer material common in fitness watches.

Patient Fitbits will be managed through Fitbit's proprietary management system. Each Fitbit will be connected to an account that is registered to a study coordinator. Using that account, the study coordinator will create Fitbit accounts for each unique user using a study gmail account. A Fitbit will then be synced to the subject account. The subject's account will be given the study ID assigned to the patient and an individual password to protect confidentiality.

The subject will wear the Charge 3 as often as they like. This will begin the collection of the subject's data. The smart watch will upload the data to the patient's phone every 15 minutes via BLE. The data is then sent to the Fitbit, where it is housed in secure Microsoft Azure servers, compliant with ISO/IEC 27001:2006 industry standards of encryption. Data sent from the phone includes the subject ID, all of the individual measurements taken by the Charge 3. This data can only be accessed by the study team.

[figure not shown]
Additional details of this device are provided below.

### Wear Charge 3

Place Charge 3 around your wrist.

[figure not shown]
Placement for all-day wear vs exercise

When you're not exercising, wear Charge 3 a finger's width below your wrist bone.

For optimized heart-rate tracking while exercising:

- Try wearing Charge 3 higher on your wrist during exercise for an improved fit and more accurate heart-rate reading. Many exercises, such as bike riding or weight lifting, cause you to bend your wrist frequently, which can interfere with the heart-rate signal if the tracker is lower on your wrist.

- Make sure the tracker is in contact with your skin.

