#### Adjust your heart-rate setting

Track your heart rate day and night with Charge 3. To preserve battery life, turn off heart-rate tracking in the Settings app > **Heart Rate**.

Note that the green LED on the back of Charge 3 continues to flash even if you turn off heart-rate tracking.

For more information about adjusting the heart-rate tracker, see [help.fitbit.com](https://help.fitbit.com).

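### The motif count for wearable activity has no denominator for hours worn or days observed, so it mixes exposure with behaviour

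*Combined protocol and SAP*

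**What the plan says.** - **Activity summary.** Section 5.13.5 reduces accelerometer data by motif discovery: "A signal can then be represented by the number of times a particular motif occurs". It then derives three sleep variables (hours slept per night, wake after sleep onset, and a sleep-to-wake ratio) and ends: "The variables will be compared between arms". It names no test, offset, valid-day rule, non-wear rule or adjustment for follow-up, and no other section supplies one.
- **Wear.** Section 2.5.4 has each participant "given a wearable sensor to wear throughout the treatment period, except while in water or when charging". Appendix A says: "The subject will wear the Charge 3 as often as they like". These two instructions conflict. Section 4.11.1 also allows a subject to decline the device.
- **Length of observation.** Section 3.2.12 plans continuous measurement up to day 120. Section 5.7 assumes that 8% die before day 120.
- **The neighbouring count endpoint.** Section 5.13.6 states that utilization counts, "with adjustment for follow-up, will be compared between arms", will be analysed by Poisson regression.

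**The concern.** The number of motifs found in a recording grows with its length. Two people with identical habits get different counts if one wears the device for longer each day or is observed for more days. Section 5.13.6 handles this for hospital days and visits; section 5.13.5 does not handle it for motifs.

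The consequence depends on whether exposure is balanced. If worn hours and follow-up have the same distribution in both arms, the test keeps its level and the cost is lost precision. If they differ, equal behaviour shows up as a difference between arms. Participants know their arm (section 5.5), and only intervention caregivers receive app components A to D rather than D alone (Appendix B). More engagement with the study platform, and so more wear, is therefore a plausible route among caregivers. Among patients, an arm with more early deaths would tend to look less active.

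**Working it through.** The plan gives no wear time, motif rate, sample size or power for this endpoint, so there is no stated figure to reproduce.

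**Identity.** Expected count = motifs per worn hour × hours worn per day × days observed. At the same rate and daily wear, a participant recorded for 40 of 120 days has 40/120 = one third of the full count.

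**Inputs from the documents.** Section 5.7 gives 83 enrolled per arm with losses of 5%, 8% and 10%: 83 × 0.95 × 0.92 × 0.90 = 65.3, hence 65 per arm. The same section requires 67 per arm. The 260 planned adult dyads give at most 130 per arm, before any attrition.

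**Assumptions not in the documents.** Mean wear, its spread, the between-person coefficient of variation (CV) of the motif rate, and the test.

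**Equal wear: loss of precision.** Take mean wear 0.75 of the period with SD 0.20, so CV² of wear = 0.04/0.5625 = 0.0711. If rate and wear are independent, CV² of the count = (1 + CV² of rate)(1 + CV² of wear) − 1.
- Rate CV 0.35: 1.1225 × 1.0711 − 1 = 0.202, against 0.1225 for the rate alone; relative variance is 1.65 times as large.
- Rate CV 0.7: 1.49 × 1.0711 − 1 = 0.596, against 0.49; 1.22 times as large.

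**Unequal wear: false positives.** 20,000 simulated trials per scenario with the same behaviour in both arms; lognormal rate with mean 1, beta-distributed wear fraction with SD 0.20, count = rate × wear, two-sample t-test at 0.05, 65 per arm:

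| Mean wear | Count, rate CV 0.35 | Count, rate CV 0.7 | Rate per worn hour |
|---|---|---|---|
| 75% vs 75% | 5% | 5% | 5% |
| 75% vs 80% | 13% | 8% | 5% |
| 75% vs 85% | 37% | 16% | 5% |
| 70% vs 85% | about 70% | 31% | 5% |

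**Second set of assumptions.** Gamma rate with CV 0.5, daily wear with CV 0.3 capped at 24 hours, Poisson counts, deaths uniform over 120 days (8% in each arm unless stated), rank-sum test at 0.05, 2,000 trials per scenario:

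| Scenario | 67 per arm | 130 per arm |
|---|---|---|
| Equal wear and deaths | 4% | 6% |
| Wear 17.6 vs 16 h/day | 12% | 19% |
| Wear 19.2 vs 16 h/day | 29% | 51% |
| Wear 20 vs 16 h/day | 40% | 69% |
| Equal wear, deaths 4% vs 12% | 7% | 10% |

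The rate per worn hour stays at 4% to 6% in every row.

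**Deaths alone.** With 8% dying uniformly over the window, mean observable time is 120 × (0.92 + 0.08 × 0.5) = 115.2 days. A 4% versus 12% split gives 117.6 versus 112.8 days, a ratio of 1.04.

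**The case against.** Several objections have force.

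- **The text describes a technique.** It says how a signal can be represented; it does not commit to an undivided 120-day total, and the unit of signal (day, window or whole period) is not stated. A reader might infer that a raw total is definitely planned. The documents support only that no denominator is given. If one is intended, writing it down settles the point.
- **The comparison sentence directly follows the sleep variables.** Those are per-night or ratio measures and do not grow with days recorded. A reader might extend the concern to them, but nothing says that unworn nights would be scored as short sleep. Only a rule for which nights count is missing.
- **Unequal wear is not shown.** Both arms receive a Fitbit and component D, which displays sleep and step data, and section 2.5.1 provides weekly coordinator contact for all dyads. Patients in both arms see the control version of the app, so the richer-app argument reaches caregivers only.
- **Some routes are weak.** Deaths move the result little. Someone who declines the device has no data rather than a low count, and section 4.9 provides for deleting a withdrawn participant's data.
- **The percentages depend on the inputs.** Doubling the assumed rate CV roughly halves the larger ones. The rate holds its level because the simulations make behaviour per worn hour independent of wear.

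What stands is that a motif count without a denominator carries exposure, exposure will vary between people under either wear instruction, and the plan already makes the corresponding adjustment in section 5.13.6.

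**Conclusion.** The point holds for the motif counts. As written, section 5.13.5 allows an arm comparison that reflects hours worn and days observed as well as behaviour. With balanced exposure the cost is precision: 1.22 to 1.65 times the relative variance under the assumptions above. With unbalanced wear the comparison is biased: at 65 per arm and 75% versus 85% mean wear, false positives are about 16% to 37% as the assumed rate CV goes from 0.7 to 0.35. Differential death alone is a small effect, about 7% to 10% for a 4% versus 12% split.

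A reader might conclude that the activity result will be biased. The documents do not support that, because they contain no wear data by arm. Activity is an exploratory endpoint (sections 2.3.2.6 and 3.2.12), so the primary analysis of caregiver quality of life is unaffected. The change is worth making because it is cheap and removes an avoidable ambiguity.

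**What to change.** In section 5.13.5:

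1. Analyse motif occurrences per recorded worn hour, or fit a count model with log worn hours as the offset.
2. State how worn time is derived, and report worn hours by arm, separately for caregivers and patients.
3. Compute the per-night sleep variables only on nights with recorded wear.

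Also reconcile the wear instructions in section 2.5.4 and Appendix A.

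The sponsor should choose the wear rule. A reader might infer that heart-rate signal is the natural marker, but the appended device guide says "To preserve battery life, turn off heart-rate tracking in the Settings app", and section 2.5.4 lets participants use a Fitbit of their own. The documents do not establish that heart rate will be available for everyone, and they support no particular minimum of hours per day. The core fix needs neither.

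The cost is revised SAP wording and one derived wear variable. Little-worn days or nights would be dropped. A rate also does not correct for people who wear the device selectively when active, so worn hours by arm should be read alongside the result.

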#### 5.13.6 Caregiver and patient health care utilization

The total count of hospital days, ED visits, readmissions, and ambulatory care clinic visits within the first 120 days post-BMT, with adjustment for follow-up, will be compared between arms using a Poisson regression model, with adjustment for potential mediating or moderating effects of patient or caregiver characteristics, if needed. The data will be captured at the time of PRO assessments. Subjects will remain in follow-up for 1-year post-HCT. The study team will have access to the electronic medical record for 1-year post-HCT.

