### **5.4 Randomization**

Blocked randomization will be used to limit bias and achieve an equal distribution of participants to the treatment and control arms. This approach will recruit participants in small blocks to ensure that half of the participants within each block will be allocated to the treatment and the other half to the control. The size of the blocks will be permuted to limit selection bias, and within each block, the

order of patients will be random. Randomization will be stratified by type of transplant (adult allo, adult auto, pediatric), so that three separate randomization lists will be created. The study statistician, [name] (Co-I), will create the randomization lists before the study begins enrollment using the statistical package R. Assignments will be allocated in list order, and an assignment will not be reused with future patients if a patient later declines to participate after being randomized. Adequate training will be given to the Project Manager and Research Coordinator, including enrollment of participants, allocation of treatment arm, and training the participants.

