## **5.7 Sample Size Considerations**

The power calculation was completed by [name] using simulations in the statistical package R. Our primary endpoint (i.e., caregiver health-related quality of life from the PROMIS® Global Health scale) is focused solely on this outcome in caregivers, while our secondary endpoints are based on outcomes for both caregivers and patients. Given this, we determined our sample size based solely on caregivers. The age- and sex-adjusted norm for the Global Health scale is 50 points, with a standard deviation of 10 points. These statistics have been shown to be generalizable to the allogeneic BMT population. Our study will have power of 0.80, assuming a two-sided Type I error rate of 0.05, to detect an effect size of 0.5 between the intervention and control arms if 67 caregivers are enrolled in each arm. A mean difference of one-half a standard deviation is biologically meaningful

and is considered a medium effect size for clinical trials. We will accrue a total of 83 caregivers in each arm to account for dropout, assuming a 5% failure to undergo BMT, 8% death before day 120, and 10% missing day 120 PRO from participants. These percentages are inflated but based on adjustments of published BMT data.

Because our main goal is to assess the primary objective in adult allo dyads, we plan accrue approximately 260 dyads with adult patients, as that is the expected number of total adult dyads needed to enroll at least 166 allo dyads. We also plan to enroll approximately 40 dyads with pediatric patients in the time it takes to enroll the 260 adult dyads.

PROMIS® measures use Item Response Theory (IRT), a family of statistical models that link individual questions to a presumed underlying trait or concept of global health represented by all items in the scale. PROMIS® instruments are scored using item-level calibrations. The most accurate way to score a PROMIS® instrument is to use the HealthMeasures Scoring Service, which our Study Team has experience with ([name], Co-I and [name], Co-I). This method of scoring uses “response pattern scoring,” which uses responses to each item for each participant. Response pattern scoring is especially useful when there is missing data (i.e., a respondent skipped an item), or different groups of participants responded to different items).

There are four key features of the score for PROMIS® Global Health:

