## **5.11 Analysis of Primary Endpoint**

Analysis will be an intent-to-treat analysis that includes all caregivers. Mean Global Health scores for each arm at day 120 will be compared using a two-sample *t*-test (or Wilcoxon Rank Sum test if non-normality is apparent) with a significance level of 0.05. Linear regression models will be performed to complement the results of the *t*-test and adjust for specific baseline caregiver characteristics (e.g., demographic, social, environmental) to increase the precision of our inference. We plan to do analyses separately for allo dyads, auto dyads, and pediatric dyads, although we have only powered the study for the analysis in the allo dyads. There is a possibility that patient characteristics will be unbalanced since our randomization scheme will be applied to caregivers. Thus, our models also will assess potential moderating or mediating effects, described below.

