## **5.12 Analysis of Secondary Endpoint**

Mean Profile 29+2 scores for each arm at day 120 will be compared using a two-sample *t*-test (or Wilcoxon Rank Sum test if non-normality is apparent) with a significance level of 0.05. Linear regression models will be performed to

complement the results of the *t*-test and adjust for specific baseline caregiver characteristics (e.g., demographic, social, environmental) to increase the precision of our inference. There is a possibility that patient characteristics will be unbalanced since our randomization scheme will be applied to caregivers. Thus, our models also will assess potential moderating or mediating effects, described below.

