### **5.13.2 Caregiver and patient PROs (see Appendix C)**

All questionnaires will be scored according to coding manuals. The resulting scores will be compared between arms at baseline and days 30 and 120 using the Wilcoxon Rank Sum test. Outcome measures will be compared between arms using linear regression modeling of day 30 and day 120 outcomes after adjusting for baseline scores. We also will model the outcomes from all three time points simultaneously using a linear mixed model to account for within-subject correlation, as well as adjust for possible moderating or mediating characteristics of the caregiver or patient.

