### **5.13.3 Caregiver and patient overall survival**

Death from any cause will be calculated from randomization to death or loss to follow-up. Participants alive at last follow-up will be censored. Survival curves will be calculated for each arm using the methods of Kaplan and Meier and will be compared between arms using the log-rank test.

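### Transplant type stratifies the randomization but is not named in the secondary and exploratory arm comparisons: a minor loss of precision for scores, and for the utilization counts a stratum term helps only alongside a corrected variance

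*Combined protocol and SAP*

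**What the plan says.** Section 5.4: "Randomization will be stratified by type of transplant (adult allo, adult auto, pediatric), so that three separate randomization lists will be created". The primary analysis follows that design; in 5.11, "We plan to do analyses separately for allo dyads, auto dyads, and pediatric dyads".

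The other comparisons do not carry it forward:

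- 5.12 (secondary): "Mean Profile 29+2 scores for each arm at day 120 will be compared using a two-sample" t-test at level 0.05, or a Wilcoxon test. Supporting regressions adjust for baseline caregiver characteristics. The 5.11 sentence on separate allo, auto and pediatric analyses is absent.
- 5.13.2 (PROs): "The resulting scores will be compared between arms at baseline and days 30 and 120 using the Wilcoxon Rank Sum test". Regressions of the day 30 and day 120 scores adjust for baseline score. A mixed model allows for possible moderators or mediators on the caregiver or patient side, none of them named.
- 5.13.3 (survival): the curves "will be compared between arms using the log-rank test", with no strata mentioned.
- 5.13.6 (utilization): counts "will be compared between arms using a Poisson regression model, with adjustment for potential mediating or moderating effects", and only where that is judged necessary.

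Section 5.10.1 analyses caregivers of adult patients apart from caregivers of pediatric patients for the primary and secondary endpoints. Section 5.10.2 applies the same analysis population to the exploratory endpoints.

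**The concern.** Blocking within transplant type removes between-type differences from the arm contrast. A test that ignores the strata still counts those differences as noise. Its standard error is then larger than the design warrants, so it rejects too rarely under the null and loses power when there is an effect.

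Allo and auto patients could plausibly differ in hospital days, visits, survival and patient-reported scores, and these are the outcomes analysed without the factor. Transplant type is known for every dyad at randomization. Leaving its use open in 5.13.2 and 5.13.6 also makes it a choice taken after the data are seen, by statisticians who are not blinded (5.5).

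**Working it through.** **Plan's own figure.** Section 5.7: "Our study will have power of 0.80, assuming a two-sided Type I error rate of 0.05, to detect an effect size of 0.5" with 67 caregivers per arm. An exact t-test needs 63.77 per arm. Dividing by the Wilcoxon efficiency 3/π gives 66.8, so 67 reproduces. Power at 67 per arm is 0.819 (t-test) or 0.801 (Wilcoxon). This is the allo comparison, which lies within one list and is not touched by this point.

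**Inputs.** Adult allo at least 166 and adult total 260 (synopsis, 5.7), so auto is about 260 − 166 = 94; shares 0.638 and 0.362. Pediatric 40. Allocation 1:1 within blocks (5.4). The documents give no outcome means by stratum, so every stratum difference below is an assumption shown as a range. Only 5.12 states a 0.05 level; it is assumed for the exploratory tests.

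**1. Scores (t-test; approximately also rank, linear and mixed models).** Let R² be the share of outcome variance between strata, and let nominal power be 80% (1.96 + 0.84 = 2.80).

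- Type I error, unstratified: 2[1 − Φ(1.96/√(1−R²))]
- Power, unstratified: 1 − Φ((1.96 − 2.80)/√(1−R²))
- Power, stratified: 1 − Φ(1.96 − 2.80/√(1−R²))

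| R² | Type I error, unstratified | Power, unstratified | Power, stratified | Loss (points) |
|---|---|---|---|---|
| 0.05 | 0.044 | 0.806 | 0.819 | 1.4 |
| 0.10 | 0.039 | 0.812 | 0.839 | 2.7 |
| 0.20 | 0.028 | 0.826 | 0.879 | 5.3 |

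For an allo–auto gap of d within-stratum SDs, v = 0.638 × 0.362 × d² and R² = v/(1+v). A gap of 0.5 SD gives 0.055 and 1 SD gives 0.188. R² = 0.20 needs d = √(0.25/0.231) = 1.04.

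*Profile 29+2 in adult caregivers*, borrowing the SD of 10 that 5.7 gives for Global Health. Evaluable per arm is 130 × 0.95 × 0.92 × 0.90 = 102.3, and SE = 10√(2/102.3) = 1.40. For a 5-point arm effect, stratified power is 0.947. For allo–auto gaps of 2, 5 and 10 points:

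- the unstratified SE is 1.005, 1.028 and 1.109 times the stratified SE;
- type I error is 0.049, 0.044 and 0.030;
- power is 0.946, 0.941 and 0.919.

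**2. Log-rank.** Simulated with 166/94/40 dyads, assumed 120-day death risks from 8/8/8% to 12/2/6%, hazard ratio 0.4, 1,500 runs each. Power is 0.42–0.43 unstratified and 0.42–0.44 stratified. At the 8% risk in 5.7 there are only about 300 × 0.08 = 24 deaths.

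**3. Utilization counts, plain Poisson as written.** With equal arms, the model-based SE of the log rate ratio is √(2/events per arm), with or without a stratum term. At assumed adult means of 40 (allo) and 20 (auto) hospital days, events per arm are (166×40 + 94×20)/2 = 4,260, so SE = √(2/4260) = 0.0217. Simulation gave 0.0217 with the term and 0.0217 without it.

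Now assume overdispersion (gamma CV 0.5, variance μ + 0.25μ²). Within-stratum variances are 440 and 120. The summed variance per arm is 83×440 + 47×120 = 42,160, and the true SE is √2 × √42,160/4,260 = 0.068, about 3.1 times the model's. Type I error is 2[1 − Φ(1.96/3.14)] ≈ 0.53. Across means of 30/25 to 40/20, simulated null rejection was 0.47 to 0.53 with or without the term.

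**4. Counts with a robust (sandwich) SE.** Same adult setting, 4,000 runs, arm log ratio −0.18:

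| Allo/auto means | Power without / with stratum | Null rejection without / with stratum |
|---|---|---|
| 30/25 | 0.763 / 0.770 | 0.050 / 0.053 |
| 30/20 | 0.726 / 0.759 | 0.041 / 0.054 |
| 35/20 | 0.687 / 0.750 | 0.034 / 0.051 |
| 40/20 | 0.660 / 0.749 | 0.030 / 0.053 |

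The stratum term earns its place here, but only after the variance is corrected.

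**The case against.** The strongest objection concerns utilization. A reader might infer that, as written, the utilization intervals are too wide and the test conservative. The documents do not support that. Section 5.13.6 specifies a Poisson model and no robust variance, and steps 3 and 4 show that under overdispersion its intervals are too narrow, whatever is done about strata. A stratum term alone would leave that error in place. This objection stands in full and shapes the fix.

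Three others stand in part:

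- The adult/pediatric split in 5.10.1 already separates one stratum for Profile 29+2, and through 5.10.2 arguably for the exploratory endpoints. But it speaks only of caregivers, while 5.13.2, 5.13.3 and 5.13.6 also cover patients. Appendix D gives pediatric patients different forms, so several patient PROs would not be pooled with adults anyway. Allo and auto remain pooled on any reading.
- The baseline-score adjustment in 5.13.2 may absorb some of the stratum difference, and its reference to patient characteristics could accommodate transplant type. It does not commit to it.
- A power loss of 5 points needs an allo–auto gap of about 1 SD. Nothing in the documents suggests so large a gap in caregiver scores.

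A reader might also infer inflated type I error for the score comparisons, or a threat to the main result. Neither follows. Ignoring the strata is conservative for scores, and the primary tests are run within each transplant type.

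**Conclusion.** The inconsistency is real and minor. Sections 5.12, 5.13.2, 5.13.3 and 5.13.6 do not name the factor on which the trial is randomized, and adult allo and auto dyads are pooled.

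- **Scores:** somewhat conservative, with type I error 0.044 to 0.028 and a power loss of about 1 to 5 points, for assumed R² of 0.05 to 0.20.
- **Survival:** negligible.
- **Utilization:** no effect on the plain Poisson SE. The gain, about 1 to 9 points over the assumed means in step 4, appears only with a corrected variance.

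The sizes rest on assumed stratum differences and overdispersion; the directions do not depend on the exact values chosen. Only secondary and exploratory comparisons are involved.

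**What to change.** State in 5.10.2 that every arm comparison pooling more than one randomization list accounts for transplant type (adult allo, adult auto, pediatric), and say whether the adult/pediatric split applies to exploratory and patient outcomes. Then:

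- 5.12 and 5.13.2: transplant type as a fixed covariate in the linear and mixed models, and the van Elteren form in place of the plain Wilcoxon test. In 5.12, base the comparison of means on the stratum-adjusted model.
- 5.13.3: a log-rank test stratified by transplant type, for consistency with the design rather than for power.
- 5.13.6: transplant type as a fixed covariate, not optional, together with a robust (sandwich), quasi-Poisson or negative-binomial variance. The two changes belong together.

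The cost is SAP wording and at most two degrees of freedom per model. The factor is already recorded, so no new data are needed. The pediatric stratum of about 40 dyads will contribute little to the survival comparison.

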## 2.5 Intervention Plan

### 2.5.1 How will the intervention work?

Participants (caregiver-patient dyads) who are consented, enrolled, and randomized will be scheduled for a one-hour training session with the Research Coordinator(s) prior to or during admission to undergo the HCT. Based on our experience, these training sessions will be coordinated with other clinic appointments at the hospital in efforts to minimize burden on the caregiver and patient or remotely via institutionally approved virtual meeting platform. Once the intervention has begun, the Research Coordinator(s) will meet with the participants (caregiver-patient dyad) weekly to review any questions or concerns, to perform data download (wearable sensor device), and to ensure adherence to the protocol. HCT patients are typically inpatient for approximately four weeks. During this period, the Research Coordinator(s) will be available by pager and will schedule weekly visits with the participants or virtual visits. Once discharged, HCT patients return to clinic on a weekly visit in the ambulatory care setting. The Research Coordinator will meet with participants during those routine appointments. Roadmap 2.0 software will be maintained in collaboration with Arbormoon Software, Inc.

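### The Poisson comparison of health care utilization in section 5.13.6 specifies no protection against overdispersion, which matters most for hospital days

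*Combined protocol and SAP*

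**What the plan says.** Section 5.13.6 takes four counts, "The total count of hospital days, ED visits, readmissions, and ambulatory care clinic visits", measured "within the first 120 days post-BMT, with adjustment for follow-up". It says that they "will be compared between arms using a Poisson regression model", "with adjustment for potential mediating or moderating effects of patient or caregiver characteristics, if needed".

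No other section adds a scale parameter, a robust variance, a negative binomial alternative or a check of the Poisson assumption. The bootstrap standard errors in section 5.13.4 are for the direct and indirect effects of the mediation analysis, not for this comparison.

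The documents give no mean, variance, sample size or power for these counts. The nearest figure is in section 2.5.1: "HCT patients are typically inpatient for approximately four weeks". Utilization is an exploratory objective (2.3.2.7) and endpoint (3.2.13). A significance level of 0.05 is stated in sections 5.7, 5.11 and 5.12, but none is stated for utilization.

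**The concern.** A Poisson model sets the variance equal to the mean. Hospital days are not separate, independent events: a single admission contributes many days at once, so patients differ by whole stays. When the true variance exceeds the mean, the Poisson standard error is too small, confidence intervals are too narrow and p-values are too low. The trial could then report that the app changes hospital use when the difference is chance.

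The other counts are less clear. ED visits and readmissions may cluster in sicker patients, but the documents do not say by how much. Section 2.5.1 describes weekly clinic visits after discharge. Counts set largely by a schedule can vary less than Poisson, and then the error runs the other way and the intervals are too wide.

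**Working it through.** **No planned figure to reproduce.** The plan gives no calculation for utilization. The 67 caregivers per arm in section 5.7 belongs to the primary endpoint and has no bearing here.

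**Inputs**
- Mean hospital days: 28, assumed from the four-week stay in section 2.5.1.
- SD of hospital days: 8, 10, 14 and 20 days, all assumed.
- Rarer events: variance-to-mean ratios of 1.3, 1.6 and 2.0, and a mean of 0.6 in the simulation, all assumed.
- Patients per arm: 83 (powered allogeneic cohort, section 5.7) and 150 (half of the 300 dyads).

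**Formula.** Write φ = variance/mean. The Poisson standard error is too small by a factor √φ, so the true two-sided error of a nominal 5% test is 2 × P(Z > 1.96/√φ).

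**Hospital days.** Under Poisson, a mean of 28 implies an SD of √28 = 5.3 days. The simulations drew gamma-Poisson counts with no arm effect (20,000 runs, 150 per arm):

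| Assumed SD | φ = SD²/28 | √φ | Error, formula | Error, simulated |
|---|---|---|---|---|
| 8 | 2.29 | 1.51 | 0.195 | 0.198 |
| 10 | 3.57 | 1.89 | 0.300 | 0.297 |
| 14 | 7.00 | 2.65 | 0.459 | 0.459 |
| 20 | 14.29 | 3.78 | 0.604 | 0.606 |

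**Why φ above 1 is expected for hospital days.** Take an assumed index stay of 25 days with an SD of 5, plus readmissions that are themselves exactly Poisson with mean 0.5, each lasting 7 days. The mean is 25 + 0.5 × 7 = 28.5. The variance is 5² + 0.5 × 7² = 49.5. So φ = 49.5/28.5 = 1.74 and the error is about 14%, with a tight index stay and no other difference between patients.

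**Rarer events.** At φ = 1.3, 1.6 and 2.0 the formula gives 0.086, 0.121 and 0.166. Simulation at mean 0.6 gives 0.081, 0.121 and 0.158.

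**Clinic visits.** If scheduling made φ = 0.5 (assumed), the formula gives 0.0056, so the test would reject about 0.6% of the time instead of 5%. If φ were 2 to 4 at a mean of 15 (also assumed), simulation at 83 per arm gives 0.17 to 0.33. The documents do not settle which applies.

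**Do sample size or follow-up adjustment help?** A second simulation used a log follow-up offset, shortened follow-up in 8% of patients and 4,000 runs per setting. For hospital days with φ of 3.6, 7 and 14, plain Poisson rejected 0.30, 0.46 and 0.61 of the time at 83 per arm, and 0.30, 0.45 and 0.60 at 150 per arm. Neither the larger sample nor the offset removes the error.

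**Does the remedy work?** In the same runs, sandwich and quasi-Poisson standard errors gave rejection rates of 0.042 to 0.061 in every setting, φ from 1 to 14. With φ = 1, plain Poisson stayed near 0.05, so robust errors cost little if the Poisson assumption happens to hold.

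**The case against.** The strongest objection is that every dispersion value above is assumed. That stands: the documents give no variance for any of the counts, so the percentages are conditional. The direction for hospital days follows from how days accumulate and does not depend on a particular value.

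The 28-day mean is also borrowed. Section 2.5.1 describes a typical inpatient stay, whereas section 5.13.6 counts days after transplant up to day 120. That count would leave out inpatient days before transplant and add readmission days. The mean is therefore a working value only.

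Differences between allogeneic, autologous and pediatric transplants are partly dealt with. Randomization is stratified by these groups (section 5.4), and section 5.11 plans separate analyses for them under the primary endpoint. Section 5.10 separates adult from pediatric caregivers for the primary and secondary endpoints and uses the same population for exploratory ones. If this carries over to utilization, that source of spread shrinks. Runs of days within a stratum remain.

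Follow-up adjustment is already planned. Patient characteristics may be added, but only if needed and without being named, and they would remove only part of the excess variance. The plan is also silent on a robust variance rather than against one; a Poisson model with sandwich errors is still a Poisson regression model. That makes the fix easy, but it leaves the choice to be made after the data are seen, by statisticians who are not blinded (section 5.5).

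Finally, the endpoint is exploratory and has no stated significance level. That stands, and it limits the consequence.

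**Conclusion.** The concern holds as a specification gap in an exploratory analysis, centred on hospital days. As written, section 5.13.6 gives valid standard errors only if variance equals the mean, which is structurally implausible for hospital days. If the mean is near 28 and the SD is 8 to 20 days (both assumed), a nominal 5% test has a true error of about 20% to 61%. For rarer events with φ of 1.3 to 2.0 (assumed), it is about 8% to 16%. The primary endpoint, its sample size and its conclusion are unaffected.

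A reader might infer that intervals will be too narrow for all four outcomes. The documents do not support that: clinic visits are largely scheduled and may be underdispersed, and nothing is known about the spread of ED visits or readmissions.

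A reader might also infer that a false claim about health care use is likely. At φ = 2, four outcomes treated as independent would give a 52% chance of at least one false positive, against 18.5% at φ = 1. That figure needs the same overdispersion in all four counts, independence between them and a 5% rule that the plan does not state for utilization. None of these is established.

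Section 5.13.6 also covers caregiver utilization. The documents give nothing from which to size the error there.

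**What to change.** In section 5.13.6, specify Poisson regression with robust (sandwich) standard errors for all four counts, or negative binomial regression where counts are overdispersed. Sandwich errors have the advantage of being valid whether the variance is above or below the mean. State the planned follow-up adjustment as a log follow-up offset. Include the randomization stratum (adult allo, adult auto, pediatric) as a covariate if the strata are pooled, and say whether they are. Report rate ratios with 95% CIs.

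This costs one line of text and a model option, with no new data, visits or patients. Intervals for overdispersed counts become wider, and correctly so. One limit: the remedy was checked at 83 and 150 per arm, not at the roughly 20 per arm that 40 pediatric dyads would give if analyzed alone.
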